**Corporate Confidential Information**

The response rates at other time points (Days 2, 8, 15, 29, 43, 57) will be reported and analyzed similarly.

Proportion of responders (90% CI) will be graphically presented at each time point, by treatment group using bar charts.

The same analysis will be performed for remission rates as well.

**Corporate Confidential Information**

At Day 85, the null hypothesis that the response rate of the LFG316 arm ( $p_{LFG}$ ) is less than Corporate Confidential Information (60%):  $H_0: p_{LFG} \leq 0.60$ , will be tested against the alternative hypothesis:  $H_1: p_{LFG} > 0.60$ . The exact (binomial) p-value will be reported. Note that no decision should be made based on this p-value.

No multiplicity adjustments are required for the primary analysis.

**Handling of missing values/censoring/discontinuations**

If a subject had missing data for any of the parameters needed to derive the responder status, a subject was:

- Considered as a responder if the subject met any of the responder criteria
- Considered as missing if all the parameters for the responder criteria were missing
- Considered as a non-responder, if the subject had at least one non-missing parameter needed for the responder criteria and had met no criteria to be considered a responder.

If a subject had missing data for any of the parameters needed to derive the remission status, a subject was:

- Considered as a remission if the subject met all of the remission criteria.
- Considered as a non-remission, if the subject did not meet at least one of the remission criteria.
- Considered as missing, if the subject met all the available remission criteria but not all the remission criteria were available.

## **7.2 Secondary Efficacy and PD endpoints**

### **7.2.1 Efficacy endpoints: Ocular assessments**

All analyses in this section will be analyzed on the Efficacy 1 analysis set.

For vitreous haze score (VHS), the number and percentage of subjects will be listed by score (0, 0.5/Trace, 1+, 2+, 3+, 4+) for each visit/time and treatment group, separately for the study eye and the fellow eye. The number and percentage of subjects will also be listed by steps of improvement/worsening (change) from baseline in seven categories ("worsening of vitreous

haze score”, “no change”, and “1 – 5 steps of improvement”). The same analysis will be performed for anterior chamber cells score (ACCS) with the scores being 0, 0.5, 1, 2, 3, 4, and the category of improvement/worsening (change) from baseline being “worsening of anterior chamber cells”, “no change”, and “1 – 5 steps of improvement”. Frequency tables and histograms for both of the original scores and steps of change will be provided for VHS and ACCS by eye (study and fellow), treatment group at each visit/time.

Visual acuity will be listed for each visit/time and treatment group, separately for the study eye and the fellow eye. Summary statistics will be provided for the raw and the change from baseline of best corrected visual acuity by visit/time and treatment group, separately for the study eye and fellow eye. Arithmetic mean (SE) will be plotted across time by treatment (overlaid) for study eyes and fellow eyes separately. Overlaying individual profiles will be plotted across time by treatment (separate) for study eyes and fellow eyes separately.

A longitudinal analysis of best corrected visual acuity will be performed for the study eye. Absolute change from baseline will be analyzed by a mixed model with repeated measurements. The independent variables will be treatment, time (categorical, i.e. visits until Day 85), and treatment-by-time interaction, with baseline and baseline-by-time interaction as covariates, and subject as a random effect. Within treatment arm estimates and 90% confidence interval will be reported. A time plot for least square means and 90% CI by treatment (overlaid) will be provided.

Proportion of patients with presence or absence of macular edema, chorioretinal lesions, will be tabulated using frequency tables, and graphically represented using bar charts, at each visit, by eye (separate).

Percentage of patients that respond per response criterion (for criterion involving central retinal thickness, only if applicable) will be reported in each treatment group.

A separate set of summary tables will be produced for those subjects who participate in the LFG316 treatment extension, if deemed necessary.

### **7.2.2 PD endpoint: Total C5 Concentrations**

Total C5 will be analyzed on the PD analysis set. Summary statistics of total C5 concentrations will be provided by treatment and visit/time. Total C5 concentrations will be expressed as  $\mu\text{g/mL}$ . All concentrations below the limit of quantification (LLOQ) or missing data will be labeled as such in the concentration data listings. Concentrations below the LLOQ will be treated as zero in summary statistics for concentration data only.

Arithmetic mean (SD) concentration-time plots as well as overlaying individual concentration-time profiles will be provided.

## Corporate Confidential Information

### **7.4 Handling of Missing values/censoring/discontinuations**

Missing values will not be imputed, but treated as “missing at random” in the primary and secondary analyses.

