## **7 Statistical methods for Efficacy and Pharmacodynamic (PD) parameters**

### **7.1 Primary endpoint**

The primary endpoints are the response rate (proportion of patients that respond in the study eye) and the remission rate (complete response) at Day 85.

A response will be defined by any one of the following criteria in the study eye:

- An improvement of 2 or more steps in vitreous haze, relative to baseline. For the purpose of “step” calculation, 0.5 shall count as one of the increments. Thus, improvement from a score of 2 to 0.5 or from 1 to 0 would constitute a 2-step improvement or,
- An improvement of 10 or more letters in visual acuity, relative to baseline or,
- An improvement of 2 or more steps in anterior chamber cells, relative to baseline
- Resolution of chorioretinal lesions as determined by the investigator

Remission (complete response) will be defined as

- any patient who has a vitreous haze score of 0 or 0.5 in the study eye, who has an anterior chamber cell score of 0 and no chorioretinal lesions in the study eye and is off all immune modulatory therapy (systemic, corticosteroids and topical), without any worsening of uveitis during the trial.

The analysis of response rate and remission rate at Day 85 will be carried out on the efficacy analysis sets (Efficacy 1 and Efficacy 2), with the analysis on the Efficacy 1 analysis set being of primary interest.

The baseline value will be defined as Day 1 pre-dose value, or the screening values if the Day 1 pre-dose value does not exist.

The response rates and the 90% exact (Clopper-Pearson) confidence intervals in the LFG316 group Corporate Confidential Information will be reported. Corporate Confidential Information

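### The Day 85 response rate leaves out patients with no usable Day 85 data, so likely failures can drop from the denominator; SAP 7.4 also disagrees with SAP 7.1 in one case of partial data

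*SAP*

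**What the plan says.** SAP 7.4 is a single general sentence: "Missing values will not be imputed, but treated as" missing at random, "in the primary and secondary analyses". It therefore covers the Day 85 response and remission rates.

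SAP 7.1, under its own missing-data heading, gives three rules for response when data are missing:

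- "Considered as a responder if the subject met any of the responder criteria"
- "Considered as a non-responder, if the subject had at least one non-missing parameter needed for the responder criteria and had met no criteria"
- "Considered as missing if all the parameters for the responder criteria were missing"

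For remission, a patient who fails any criterion is a non-remission. The incomplete case is left open: "Considered as missing, if the subject met all the available remission criteria but not all the remission criteria were available".

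Both rates are analysed on Efficacy 1 and Efficacy 2, "with the analysis on the Efficacy 1 analysis set being of primary interest". SAP Section 5 states that a patient in Efficacy 1 who discontinues after at least one dose contributes data only up to discontinuation or rescue medication. Efficacy 2 requires an evaluable Day 85 endpoint. The reported summaries are the rate with a 90% Clopper-Pearson interval and an exact binomial p-value against 60%. The SAP says no decision is to be based on that p-value.

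**The concern.** There are two problems, and the second matters more.

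First, response needs only one criterion. A patient with some components unobserved and none met so far has an unknown status, and scoring that patient a non-responder imputes failure. SAP 7.4 says nothing is imputed in the primary analysis. An analyst who follows 7.4 literally would leave that patient out, while one who follows 7.1 would keep the patient in the denominator.

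Second, missing at random is a property that an analysis must use. The mixed model for best corrected visual acuity in SAP 7.2.1 can use it, because earlier visits inform the later ones. A Clopper-Pearson proportion at Day 85 uses no earlier visits and no covariates. Leaving out patients with no Day 85 components is unbiased only if missingness is unrelated to response. That is doubtful here. Protocol Section 5.5.6.1 ties study-eye rescue to loss of vision from worsening uveitis or to significantly worse inflammation. With Efficacy 1 data cut at rescue, such a patient can have no usable Day 85 value, and 7.1 then removes the patient instead of counting a failure. The result is an upward bias in the headline rate of a 16-patient arm.

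**Working it through.** **Inputs.** The LFG316 arm has 16 patients and the reference rate is 60% (Protocol synopsis, sample size determination). The interval is a 90% Clopper-Pearson interval (SAP 7.1). The documents state no missing-data rate, so the number k of affected patients is an assumption, taken from 0 to 4.

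**The plan's own figures.** With n = 16, the exact tail P(X ≥ 12) is 0.167 at p = 0.60 and 0.450, 0.798 and 0.921 at p = 0.70, 0.80 and 0.85. These match the stated 17% and 45% (80%, 92%). At X ≥ 11 the values are 0.329 and 0.660, 0.918 and 0.977, which do not match. The stated figures therefore correspond to more than 11 of 16; a comparison sign may have been lost in the PDF text. They do not depend on the missing-data rule.

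**Where 7.1 and 7.4 differ for response.**

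| Day 85 data | SAP 7.1 | SAP 7.4 read literally | Conflict |
|---|---|---|---|
| Some missing, a criterion met | Responder | Responder, nothing to impute | No |
| Some missing, no observed criterion met | Non-responder | Left missing | Yes |
| All missing | Missing | Missing | No |

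The remission rule imputes nothing and agrees with 7.4.

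**Effect on the rate and interval.** Let R be the number of responders. If the k affected patients count as non-responders, the rate is R/16. If they are left out, it is R/(16 − k). The arithmetic is the same whether they are partly missing with no criterion met or have no Day 85 data. The Clopper-Pearson limits for x of n are the 5% quantile of Beta(x, n − x + 1) and the 95% quantile of Beta(x + 1, n − x); the upper limit is 1 when x = n.

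With R = 12, counting them as non-responders gives 12/16 = 75.0% (51.6 to 91.0) for every k. Leaving them out gives:

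| k left out | Rate | 90% CI |
|---|---|---|
| 0 | 12/16 = 75.0% | 51.6 to 91.0 |
| 1 | 12/15 = 80.0% | 56.0 to 94.3 |
| 2 | 12/14 = 85.7% | 61.5 to 97.4 |
| 3 | 12/13 = 92.3% | 68.4 to 99.6 |
| 4 | 12/12 = 100% | 77.9 to 100 |

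With R = 11 and k = 1, the rates are 11/16 = 68.8% (45.2 to 86.8) and 11/15 = 73.3% (48.9 to 90.3).

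**Effect on the p-value, for illustration only.** Suppose the true rate over all 16 is 60% and every dropout is a failure. The completers' rate is then 0.60 × 16/(16 − k). Take the chance of an exact p at or below 0.167:

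- k = 1: the completers' rate is 9.6/15 = 0.64. Both rules need 12 responders, and the chance is 15.3% under each.
- k = 2: the completers' rate is 9.6/14 = 0.686. The observed-case rule needs 11 of 14 (31.3%); the non-responder rule needs 12 of 16 (13.5%).

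The gap opens at k = 2 because the critical value falls from 12 to 11.

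**The case against.** The strongest reply is that the two sections fit together. SAP 7.1 is specific to this endpoint and sits under its own missing-data heading. SAP 7.4 is a general line. On that view 7.1 derives the responder status and 7.4 covers a status that is still missing. This is a sensible reading and probably the intended one, but the SAP does not state it. It also leaves the second problem untouched, because a status that is still missing is simply dropped from the proportion.

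A reader might infer that the primary analysis has two competing rules throughout, with every partly missing patient scored a failure. The documents do not support that. Patients who meet any observed criterion are responders, leaving fully missing patients as missing agrees with 7.4, and the remission rule imputes nothing. The direct contradiction is one case. A reader might also take 31% against 13% as an inflated error rate. It is not an error rate of any stated decision, since the SAP rests no decision on the p-value, and with one dropout there is no gap.

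Three further points reduce the concern without removing it:

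- Patients who stop LFG316 or are rescued are asked to attend the remaining visits (Protocol Sections 5.5.6.1 and 6), and some who discontinue may be replaced. Attendance does not help if the Efficacy 1 cut discards the later values.
- SAP 7.5, Supportive analyses, is listed in the contents but blacked out in the body, as are parts of 7.1. A sensitivity analysis may already exist there.
- With 16 patients the intervals are wide, and a shift of about 5 points lies well inside them. The shift still runs in one direction if the patients left out are failures.

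**Conclusion.** The point holds in limited form. SAP 7.1 and 7.4 contradict each other for response in one case, partly missing with no observed criterion met, and no precedence is visible. The more important weakness is that patients with no usable Day 85 data, including those whose data are cut at discontinuation or rescue, can leave the denominator. The missing-at-random label does not protect an observed-case proportion against that.

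At 12 responders, one patient left out moves the rate from 75.0% to 80.0%, and two move it to 85.7%. These sizes rest on assumed counts; with none affected, the choices agree. The upward bias further assumes that the patients left out are mostly failures, which the rescue criteria make plausible but the documents do not quantify. That a rescued patient ends up with no Day 85 value is an inference from the Efficacy 1 definition, since the visible SAP does not spell it out. The effect is on the reported rate and interval, not on a formal decision. This is a cheap improvement.

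**What to change.** 1. State in SAP 7.4 that 7.1 governs response and remission, and limit 7.4 to the visual acuity mixed model and other continuous summaries.
2. In 7.1, count Efficacy 1 patients with no usable Day 85 data as non-responders, and say explicitly that this includes data cut at rescue or discontinuation.
3. Report the observed-case rate with its 90% interval as a sensitivity analysis, unless the blacked-out SAP 7.5 already does so. Efficacy 2 does not replace a non-responder analysis, because it requires an evaluable Day 85 endpoint.

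The cost is a few SAP sentences and one table. The headline rate may be slightly lower. For a patient rescued only because of the fellow eye, non-responder scoring is conservative; the observed-case table shows the effect of leaving such patients out. The change should be made before database lock, so that the choice cannot follow the data.

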## Corporate Confidential Information

## **8 Statistical methods for safety and tolerability data**

All subjects in the safety analysis set will be included in the safety data analysis.

### **Subject demographics and other baseline characteristics**

All data for background and demographic variables will be listed by treatment and subject. Summary statistics will be provided by treatment.

Relevant medical history, current medical conditions, results of laboratory screens, drug tests and any other relevant information will be listed by treatment and subject.

### **Adverse events**

All information obtained on adverse events will be listed by treatment group and subject, separately for ocular and non-ocular adverse events. For ocular adverse events, the eye(s) involved (study/fellow/both eyes) will be reported in the listings. Time since start of IVT injection will be indicated in the listing.

The number and percentage of patients with adverse events will be tabulated by body system and preferred term with a breakdown by treatment. A subject with multiple adverse events within a body system or preferred term will be only counted once towards the total of this body system or preferred term.

Ocular adverse events will be tabulated and summarized separately for the study eye and for the fellow (non-study) eye. An adverse event reported in both eyes will be counted in both study and fellow eyes presentations.

### Corporate Confidential Information

#### **Concomitant medications / Significant non-drug therapies**

All concomitant therapies will be listed by treatment group and subject per visit. For systemic steroids doses of the therapy needs to be captured.

#### **Vital signs**

All vital signs data will be listed by treatment, subject and visit, and if ranges are available, abnormalities (and relevant orthostatic changes) will be flagged. Summary statistics will be provided by treatment and visit/time.

#### **ECG evaluations**

All ECG data will be listed by treatment, subject and visit, abnormalities will be flagged. Summary statistics will be provided by treatment and visit.

#### **Standard clinical laboratory evaluations**

All laboratory data will be listed by treatment, subject, and visit and abnormalities will be flagged. Summary statistics will be provided by treatment and visit.

#### **Special clinical laboratory evaluations**

Not applicable.

#### **Ocular assessments**

Results from ocular assessments can be used for primary safety analysis  
Corporate Confidential Information

Ocular assessments will be listed by treatment group, and subject, with specification of the eye involved (study/fellow).

### Corporate Confidential Information

Results of other ocular assessments (Slit lamp biomicroscopy, Dilated ophthalmoscopy, Color fundus photography and sd-OCT ) will be listed and could be summarized if appropriate.

## **9 Statistical methods for Immunogenicity data**

Corporate Confidential Information

---

Corporate Confidential Information
